#### 5.0 ELIGIBILITY CRITERIA

Each of the criteria in the following section must be met in order for a patient to be considered eligible for registration. For each criterion requiring test results and dates, please record this information on the Onstudy Form or on the AL Baseline Tumor Assessment Form and submit via Medidata Rave® (see Section 14.0). Any potential eligibility issues should be addressed to the Data Operations Center in Seattle at [name] or [contact] prior to registration. **NCI policy does not allow for waiver of any eligibility criterion** http://ctep.cancer.gov/protocolDevelopment/policies\_deviations.htm.

In calculating days of tests and measurements, the day a test or measurement is done is considered Day 0. Therefore, if a test is done on a Monday, the Monday 4 weeks later would be considered Day 28. This allows for efficient patient scheduling without exceeding the guidelines. If Day 14 or 28, or 35 falls on a weekend or holiday, the limit may be extended to the next working day.

- 5.1 Disease Related Criteria
  - a. Patient must have relapsed or refractory primary systemic AL Amyloidosis, histologically-confirmed by positive Congo red stain with green birefringence on polarized light microscopy, OR characteristic appearance by electron microscopy AND confirmatory AL amyloid typing (mass spectrometry-based proteomic analysis or immunofluorescence). If there is question regarding diagnosis, consult Study Chairs prior to submission via e-mail to [contact] and [contact]. Pathology report must be submitted as indicated in Section 14.4a.
  - b. Patient must have measurable disease as defined in Section 10.1 within 28 days prior to registration. Serum  $\beta$ 2 microglobulin, Serum Quantitative Immunoglobulins (IgG, IgA, and IgM), serum free kappa and lambda, SPEP with M-protein quantification, and urine immunofixation electrophoresis must be obtained within 28 days prior to registration.
  - c. Patient must demonstrate a difference in the involved serum free light chains (kappa or lambda) versus the uninvolved serum free light chain of  $\ge$  4.5mg/dL within 28 days prior to registration.

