### AND

SGOT/AST and SGPT/ALT ≤ 4.0 x IULN

- d. Patients must have adequate renal function, as defined by:
  - Creatinine clearance (CrCl) ≥ 25 mL/min., as measured by a 24-hour urine collection or as estimated by the Cockcroft and Gault formula. The serum creatinine value used in the calculation must have been obtained within 28 days prior to registration. Estimated creatinine clearance =

(140 - age) x wt (kg) x 0.85 (if female) 72 creatinine (mg/dl)

- e. Patients must have bone marrow aspirate and biopsy within 35 days prior to registration. The following are required:
  - quantitative percent clonal plasma cell involvement,
  - standard immunophenotyping,
  - immunohistochemistry,
  - cytogenetics,
  - fluorescent in situ hybridization (FISH) (via participating site local laboratory) to assess for del 17p; t11;14; t4;14, t14;16; and del 13q.

Additionally, FISH and cytogenetic testing (normal – XY; and all abnormalities) are required to have been performed and to be reported, even if "no results" was achieved (i.e. due to too few cells in specimen). If FISH was performed, then the patient is eligible. If FISH was not performed, then patient is not eligible. Central pathology analysis will not be required, however the local pathology report and FISH/Cytogenetic data must be submitted in Medidata RAVE.

- f. Patients must have adequate bone marrow function as defined by the following within 28 days prior to registration: ANC  $\geq$  1,000 cells/mcl without growth factor support, AND platelets  $\geq$  75,000 cells/mcl.
- g. Patients must have hemoglobin  $\ge 8$  g/dL within 28 days prior to registration. Patients may have received transfusion if greater than 7 days prior to registration.
- h. Patients must have adequate cardiac function as defined by the following:
  - New York Heart Association (NYHA) < Class IV heart failure (see Section 18.2); and
  - $\overline{\text{LVEF}}$  by ECHO  $\geq$  35% within 28 days prior to registration; and
  - NT-proBNP ≤ 8500 pg/mL within 28 days prior to registration.
- i. Patients must have a Zubrod Performance Status  $\leq 2$ .
- j. Patients must not have any clinically significant uncontrolled systemic illness, including but not limited to uncontrolled, active infection requiring intravenous antibiotics, unstable angina pectoris, myocardial infarction within the past 6 months, uncontrolled cardiac arrhythmias, uncontrolled hypertension, or uncontrolled diabetes mellitus.

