#### Table 1: Dose Delays for Isatuximab

Treatment-related Adverse Event	Grade of Event	Management for Isatuximab	
	Grade 4	Off protocol therapy.	
	
 
Dose delay is not required for anemia, unless deemed necessary by the treating physician. Transfusions and/or erythrocyte stimulating agents are allowable.
 
		
All other events	≤ Grade 1	No change.	
	Grade 2	Hold isatuximab until < Grade 2 OR patient returns to baseline (where patient had a predetermined abnormal baseline).	
	Grade 3	Hold isatuximab until < Grade 2 OR patient returns to baseline (where patient had a predetermined abnormal baseline).	
	Grade 4	Off protocol therapy.	

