#### Footnotes for Calendar 9 (Isatuximab)

- A Tests are to be performed per Section 5.1d for suspected organ involvement. If baseline test was performed and abnormality present, the tests will be repeat until off tx prior to progression.
- B See Section 15.1.
- c Prior to treatment on each day of isatuximab, or within 3 days prior to each administration.
- E See Section 7.1c for type and screen requirements. See Appendix 18.6 for sample type and screen card.
- F For women of childbearing potential, prior to beginning treatment at each cycle (or up to 3 days prior to Day 1).
- G If required: Day 1 of Cycles 1, 4, and 7, then every 3 cycles (+/- 7 days) during treatment, then every 6 months (+/- 21 days) hematologic progression.
- H If required: Day 1 of Cycles 1, 3, 5, then every 2 cycles (+/- 7 days) until completion of treatment, then every 6 months (+/- 21 days) until hematologic progression.
-  If required: Every 6 months during and after treatment until hematologic progression, then as clinically indicated.
- J TSH with reflex to free T4, and free T3 uric acid and LDH are required only when clinically indicated; however, baseline testing is encouraged to assess for thyroid involvement, if suspected.
- K See Section 7.4 for a detailed description of organ evaluation and 24 hour urine collection assessment criteria, including serum chemistry panel requirements. All evaluations will continue at specified intervals until one of the criteria for removal from protocol treatment has been met (see Section 7.5).
- L If required: Day 1 (+/- 3 days) of each cycle.
- M See treatment plan Section 7.3.
- N See Sections 5.1d.5 and 7.1b.
- o Must include assessment of soft tissue and lymph nodes, if present at baseline; see Section 7.4e.
- P May be either INR or PT and PTT. Whichever is performed at baseline should be used throughout treatment.
- Q Assessments should continue until resolution of all acute adverse events.
- R Only required per Section 5.3 Eligibility.

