11.4 Analysis of Secondary and Other Endpoints

Toxicity will be evaluated using the CTCAE Version 5.0 items. All eligible patients that have initiated treatment will be considered evaluable for toxicity analyses. The maximum Grade for each toxicity will be recorded for each patient, and frequency tables will be reviewed to determine toxicity patterns. Assuming 35 eligible, evaluable patients, any toxicity event seen with at least 5% probability is likely to be observed at least once (83% chance). With 35 eligible patients, response rates and rates of individual toxicities can be estimated to within +/- 17% (95% confidence interval).

Organ response will be evaluated in the subset of patients with evaluable organ involvement using current criteria Organ involvement will be considered evaluable if it qualifies based on the criteria defined in Section 10.3. There may be eligible patients whose organ involvement is based upon a feature (such as amyloid deposition or certain types of soft tissue involvement) that does not have an associated response/progression

definition. These patients will not be evaluated for organ response. The proportion of patients with organ response will be estimated as the number of patients with documented organ response out of the number of patients with documented evaluable organ involvement at baseline.

OS and PFS will be estimated using the Kaplan-Meier method.

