#### 13.0 REGISTRATION GUIDELINES

#### 13.1 Registration Timing

Patients must be registered prior to initiation of treatment (no more than 5 working days prior to planned start of treatment).

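### Section 11.4 tabulates maximum CTCAE grade with no entry grade beside it, so unchanged entry cytopenias can be counted as on-treatment toxicity unless sites filter them

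*Combined protocol and SAP*

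**What the plan says.** Section 11.4 evaluates toxicity with CTCAE v5.0 items in all eligible patients who started treatment. Its only summary rule is: "The maximum Grade for each toxicity will be recorded for each patient, and frequency tables will be reviewed to determine toxicity patterns". It sets no condition that a grade be new, worse than at entry, or attributed to isatuximab.

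Section 5.3 allows low counts at entry. Section 5.3f requires an ANC of at least "1,000 cells/mcl without growth factor support, AND platelets" of at least 75,000/mcl. Section 5.3g sets the hemoglobin floor at 8 g/dL and adds: "Patients may have received transfusion if greater than 7 days prior to registration". For liver tests, Section 5.3c accepts "SGOT/AST and SGPT/ALT ≤ 4.0 x IULN" and bilirubin up to 2.0 times the institutional upper limit.

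Entry values are kept. Section 5.0 says: "For each criterion requiring test results and dates, please record this information on the Onstudy Form or on the AL Baseline Tumor Assessment Form". The Section 9.0 calendar starts toxicity notation on Day 1 of Cycle 1, with nothing in the pre-study column. It does schedule a CBC and chemistry pre-study and at each dosing day, timed by footnote C: "Prior to treatment on each day of isatuximab, or within 3 days prior to each administration". Section 14.4c has the Adverse Event Form submitted after every cycle.

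Baseline is used in two other places. In Table 1, the row for all other events lets a hold end when the "patient returns to baseline (where patient had a predetermined abnormal baseline". In the Section 11.5 run-in, the cardiac item is judged partly against the patient's own NYHA baseline.

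**The concern.** Evaluating toxicity is the first secondary objective (Section 1.2a), and there is no control arm to show the background frequency of low counts. A patient who enters with a gradable hemoglobin, ANC or platelet value and stays there has, on a literal reading of Section 11.4, a maximum on-treatment grade equal to the entry grade. That patient could appear in the anemia, neutropenia or thrombocytopenia row without any change on isatuximab. The Section 3.1 risk list names anemia, neutropenia and thrombocytopenia as possible effects of the drug, so entry disease and drug effect are easily confused in these rows. A reader of the finished table could not separate them.

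**Working it through.** **1. The plan's own figures reproduce.** With n = 35 (Section 11.4):
- Chance of seeing at least once an event with 5% probability: 1 − 0.95^35 = 0.834 (stated 83%).
- Widest 95% half-width: 1.96 × √(0.25/35) = 0.166 (stated 17%).

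These figures describe sampling error. They do not address whether a counted event began before treatment.

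**2. Is there a tabulation rule elsewhere?**

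| Place | Baseline used? | Governs the 11.4 tables? |
|---|---|---|
| Section 11.4 | No | Yes |
| Table 1, all other events | Yes | No, dose holds only |
| Table 1, neutropenia and anemia rows | No | No, dose holds only |
| Section 11.5 run-in, cardiac item | Yes (NYHA) | No, accrual pause only |
| Section 16.1 expedited reporting | No rule for pre-existing abnormalities | No |

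None does. Any filter would have to come from site judgement or from form instructions that are not in the documents.

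**3. Size per patient.** One patient counted only for an unchanged entry grade adds 1/n to that row:
- n = 35 (planned evaluable): 1/35 = 2.9 points
- n = 39 (all enrolled): 1/39 = 2.6 points
- n = 20 (stopped after Stage 1): 1/20 = 5.0 points

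Six such patients in one row would add 6/35 = 17.1 points, about the stated half-width. Six is a break-even count, not a prediction.

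**4. Range under an assumed prevalence.** Let q be the share of patients entering with a gradable abnormality in one item, none of it filtered, and e the true rate of new or worse events. The any-grade row then shows q + (1 − q)e. The documents do not give q, so these values are assumptions. With e = 10%:

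| q | Row shows |
|---|---|
| 0% (or all filtered) | 10% |
| 5% | 14.5% |
| 10% | 19% |
| 20% | 28% |
| 30% | 37% |

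**5. How old can an eligibility value be at first dose?** Section 5.3 allows 28 days before registration. Section 5.0 lets a Day 28 that falls on a weekend or holiday move to the next working day, so a Saturday limit moves to Monday, giving 30 days. Section 13.1 permits registration "no more than 5 working days prior to planned start of treatment", which is 7 calendar days from a Monday. The total is 30 + 7 = 37 days, and a holiday could add more. The pre-dose draw on Cycle 1 Day 1 is at most 3 days old, so it is the better baseline where its value is captured.

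**The case against.** The strongest reply is that no harm is shown. Double counting needs sites to report unchanged entry values, and the Adverse Event Form instructions are not available. The protocol's use of the word toxicity also leans the other way: Section 1.2a ties it to treatment, Table 1 is headed as treatment-related events, and Section 8.7 speaks of suspected reactions. An investigator might well not record a stable entry anemia. This stands as a limit on size, which may be zero. It does not supply a rule, because Section 11.4 neither says this nor conditions on attribution.

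It is also fair that nothing is lost for good. The entry values are recorded, so the extra table could be produced at reporting without an amendment. That keeps the point minor.

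A reader might infer that the exposure clearly extends to AST, ALT and bilirubin, given the generous entry limits. The documents do not support this. The CTCAE v5.0 definitions are not reproduced, and if those items are graded against an abnormal baseline the problem does not arise for them. Symptomatic items are also outside the point, since no systematic pre-dose grade is specified for them.

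**Conclusion.** The point holds as a minor improvement for hemoglobin, ANC and platelets. The plan's single toxicity table cannot distinguish an entry cytopenia from one that arose on isatuximab. The size is 2.9 points per affected patient at n = 35, with the number affected unknown and possibly zero. This rests on two assumptions: that some patients enter with values that CTCAE v5.0 grades, and that sites do not screen out unchanged ones.

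Two stronger inferences are not supported. One is that the reported rates will be inflated; the documents give neither entry prevalence nor the form instructions, so only the possibility is established. The other is that decisions are at risk. The primary endpoint is hematologic response, the two-stage rule counts responses, and the run-in counts its own listed first-cycle events. None of them uses the Section 11.4 tables.

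**What to change.** In Section 11.4, keep the raw maximum-grade table and add a short rule:

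- For hemoglobin, ANC and platelets, tabulate baseline grade by worst on-treatment grade, and report the number of patients whose grade is new or worse than at entry.
- Include AST/ALT and bilirubin only if CTCAE v5.0 does not already grade them against an abnormal baseline.
- Define baseline as the last recorded value before first dose: the Cycle 1 Day 1 pre-dose value if captured, otherwise the eligibility value, which can be about 37 days old.
- Take on-treatment grades from the per-cycle Adverse Event Form. Where an item has no entry, count the patient as not worsened only if the form was received; show missing forms as unknown.
- Flag patients transfused before entry, where recorded, because their baseline hemoglobin or platelets may look better than their untransfused level.

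The cost is a few sentences, one table and the grading of entry values already recorded, with no new data collection. The downside is a little more analysis work and some misclassification, because the baseline grade comes from a laboratory value and the on-treatment grade from a site-reported form.

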#### 11.5 Safety Analysis

There is no formal Data and Safety Monitoring Committee for this study. Accrual reports are generated weekly and study-specific accrual is monitored by the Study Chair, Study Statistician and the Disease Committee Chair.

There will be a run-in to ensure safety of this treatment combination. Ten patients will initially be treated. The following adverse events of special interest are specified as a potential safety concern, if a patient experiences one of them in the 1st cycle of treatment. If two or fewer patients experience any of the toxicities listed below during the first cycle of treatment, then accrual will continue as planned. If three or more patients experience at least one of these toxicities during the first cycle of treatment, the trial will be temporarily closed to accrual pending a decision as to whether to continue accrual. If accrual is reopened, a protocol revision will include justification for continued accrual and for any treatment regimen modifications. If accrual is proceeding quickly, enrollment will be paused until all ten patients in the initial safety cohort have completed one cycle of treatment or experienced one of the events listed below.

Events to be monitored during safety run-in:

- Grade 3 and 4 infusion-associated reaction (IARs) defined as anaphylactic reaction, hypertension, or dyspnea.
- Grade 4 cardiac event (including CHF and arrhythmias) (or > 2 NYHA grades higher than patient baseline)
- Grade 4 neutropenia or thrombocytopenia that does not resolve to < Grade 3 within 10 days
- Grade 4 infection.
- Grade 4 gastrointestinal ileus, or obstruction.
- Grade 4 LFT abnormalities (AST, ALT, Bilirubin)

Reports summarizing adverse events, serious adverse events (SAEs) and treatment administration are provided monthly to the Study Chair and Study Statistician for monitoring. In addition, all SAEs, which by definition require expeditious reporting, are reviewed and processed by the Adverse Event Coordinator at the SWOG Operations Office and a physician reviewer based on data provided via the NCI CTEP-AERS system. Cumulative study-specific SAE reports are provided to the Study Chair and Study Statistician upon occurrence of an event. Formal reports summarizing the study are prepared for all SWOG members every 6 months.

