#### 2.0 BACKGROUND

2.1 Study Population

Systemic light chain (AL) amyloidosis is a monoclonal plasma cell disease in which misfolded light chains spontaneously aggregate into soluble oligomers and insoluble fibrils. Extracellular fibril deposition in different organs leads to organ dysfunction and symptoms. Historically, survival after a diagnosis of AL amyloidosis has been short, particularly in patients with advanced cardiac involvement (with a median survival of 3-6 months). (1) Current therapy for AL amyloidosis generally targets the small light chain-producing monoclonal plasma cell population in the bone marrow. Therapeutic regimens have been adapted from myeloma therapy.

Approximately 1/3 of AL patients are eligible for high-dose melphalan and autologous stem cell transplantation (ASCT), with the remaining patients generally being treated with alkylator and/or bortezomib-based regimens. The outcomes of 421 subjects treated with HDM-SCT from July 1994 to December 2008 revealed the median event-free survival (EFS) and overall survival (OS) were 2.6 and 6.3 years, respectively. Of 340 subjects, who were evaluable at 1 year beyond HDM-SCT, 43% achieved a complete response (CR) and 78% of them experienced an organ response. For CR subjects, median EFS and OS were 8.3 and 13.2 years, respectively. Among the 195 subjects who did not obtain CR, 52% reached an organ response, and the median EFS and OS were 2 and 5.9 years, respectively. (2) Cardiac involvement at diagnosis and response to therapy are the two main determinants of survival in both ASCT and non-ASCT patients.

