8.2 Supportive Care

Blood product transfusion, intravenous albumin, intravenous fluids and electrolyte replacement, antiemetics, antidiarrheal medication, g-csf, anti- hypersensitivity medications are all allowable as per institutional standards and Section 3 of the protocol.

- 8.3 Dose Delays
  - a. No dose reduction is authorized for isatuximab.
  - b. Cycle delay up to 14 days is allowed, as indicated in Table 1 below.

Any additional delay (beyond 14 days) must be determined in consultation with the Study Chair(s), and documented via email to: [contact] and [contact]. The decision to continue treatment will be based on potential for continued clinical benefit, as determined jointly by the treating physician(s) and Study Chair(s). Treatment may not be delayed for any reason for more than 42 consecutive days.

c. Within a cycle, an isatuximab administration can be delayed for up to +/-3 days. If the dose cannot be administered within +/- 3 days, the isatuximab dose will be omitted. If one dose of isatuximab is administered within these windows, the interval between the next infusions should be maintained to 1 week or 2 weeks respectively

Only 1 omission per cycle is permitted. Further omissions must be discussed on a case by case basis with the Study Chair, documented by email to: [contact] and [contact].

d. If a patient experiences several AEs and there are conflicting recommendations, follow the most conservative dose delay.

Treatment-related Adverse Event	Grade of Event	Management for Isatuximab	
Neutropenia	≤ Grade 1	No change.	
	Grade 2	No change.	
	Grade 3 Hold isatuximab until ≤ Grade 3		
	Grade 4 Off protocol therapy.		
	 G-CSF may be used per treating physician discretion and institutional guidelines. See Section 8.4 .		
Anemia 	≤ Grade 1	No change.	
	Grade 2	Hold isatuximab until < Grade 2.	
	Grade 3	Hold isatuximab until < Grade 2.	

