#### 11.0 STATISTICAL CONSIDERATIONS

11.1 Two-Stage Design

The primary goal of this study is to test the hypothesis that the rate of confirmed overall hematologic response (CR+VGPR+PR) to treatment is at most 10% versus the alternative that the true hematologic response rate is 30% or greater.

A two-stage design will be used for patient accrual, with a total of 35 eligible patients who are evaluable for hematologic response per the definition in Section 11.2b below. (24) Patients who received at least one dose of study drug will be considered evaluable. Initially, 20 eligible, evaluable patients will be accrued. If one or fewer hematologic partial or better responses are observed in the first 20 patients, this treatment will be considered insufficiently active in this population and further accrual will be terminated. If two or more confirmed, partial or better responses are observed, then an additional 15 eligible, evaluable patients will be accrued. If at least 8 out of the total 35 patients have a confirmed response, the treatment may be recommended for further testing in subsequent studies. An estimated 39 patients will be enrolled to this study (including 35 eligible and evaluable patients, with 20 enrolled to Stage 1 and 15 enrolled to Stage 2, and with an additional 4 patients enrolled overall to account for ineligible and unevaluable patients).

With an estimated accrual rate of 1-2 patients per month, it is anticipated that the study will reach full accrual in 20 to 40 months.

- 11.2 Sample size and Power Justification
  - a. Assuming the number of hematologic responses is binomially distributed this design has a significance level of 2% and a power of 87% for detecting a true overall hematologic response rate of at least 30% versus the null hypothesis response rate of 10% of less.
  - b. All eligible patients who receive any study treatment will be considered to be evaluable for response and toxicity, and will be included in the analysis.
  - c. Patients who go off study or die prior to the first response assessment will be considered as non-responders.
- 11.3 Analysis of Primary Endpoint

The primary endpoint of this study is overall confirmed hematologic response rate (ORR), which includes partial response (PR), very good partial response (VGPR) and complete response (CR) as defined in Section 10.2.

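### The safety run-in does not define who counts among its ten patients, so a patient who leaves Cycle 1 early for non-toxicity reasons would count as event-free and weaken the 3-of-10 trigger

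*Combined protocol and SAP*

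**What the plan says.** Section 11.5 starts the run-in with a plain statement of cohort size: "Ten patients will initially be treated". Two rules follow. The continue rule is "If two or fewer patients experience any of the toxicities listed below during the first cycle of treatment, then accrual will continue as planned". The closing rule is "If three or more patients experience at least one of these toxicities during the first cycle of treatment, the trial will be temporarily closed", pending a decision on whether to go on.

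One sentence concerns observation: "If accrual is proceeding quickly, enrollment will be paused until all ten patients in the initial safety cohort have completed one cycle of treatment" or have had a listed event. It is conditional on accrual being quick.

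The run-in text does not define evaluability, set a minimum exposure or give a replacement rule. The plan's general rule is in Section 11.2b: "All eligible patients who receive any study treatment will be considered to be evaluable for response and toxicity". Section 11.4 likewise makes eligible patients evaluable for toxicity once treatment has begun. For response, Section 11.2c deals with early exits explicitly and counts them as non-responders. The run-in has no counterpart.

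On exposure, the Section 7.3 table plans four infusions in the 28-day Cycle 1. Section 8.3c says "Only 1 omission per cycle is permitted", with further omissions discussed case by case with the Study Chair.

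**The concern.** A count rule with a fixed threshold is only as sensitive as the number of patients actually at risk and observed. A patient who withdraws or deteriorates after one infusion, without a listed event, adds nothing to the event count but still fills one of the ten places. For response, the plan counts early exits against the drug. For the run-in, its general evaluability rule counts them in the drug's favour.

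The run-in is the only numerical toxicity rule in the plan, and there is no formal data and safety monitoring committee. Section 2.5 says the drug has not been used in AL amyloidosis before. Section 7.5 allows withdrawal at any time and removal for symptomatic deterioration, so exits within Cycle 1 are possible, although no rate is given.

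**Working it through.** **Plan figures.** The documents give no operating characteristic for the run-in, so there is none to reproduce. Exact binomial arithmetic does reproduce the nearby figures:

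- two-stage significance level 1.99% (stated 2%) and power 86.6% (stated 87%);
- chance of seeing a 5% toxicity among 35 patients: 1 − 0.95^35 = 83.4% (stated 83%).

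**Inputs.** Cohort of 10 and trigger at 3 or more (Section 11.5). *Assumed, because not stated:* true Cycle 1 probability of a listed event, p = 20%, 30% or 40%; number of early leavers without an event, 0 to 3; share of Cycle 1 risk that leavers carried before leaving.

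**Step 1: all ten fully observed.** P(X ≥ 3) = 1 − Σ C(n,x) p^x (1−p)^(n−x) over x = 0, 1, 2. With n = 10 and p = 0.30: 1 − (0.0282 + 0.1211 + 0.2335) = 0.617.

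**Step 2: leavers carry no risk (upper bound on the loss).** With k leavers counted as event-free, n becomes 10 − k while the threshold stays at 3.

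| True rate | 0 leavers | 1 | 2 | 3 |
|---|---|---|---|---|
| 20% | 32.2% | 26.2% | 20.3% | 14.8% |
| 30% | 61.7% | 53.7% | 44.8% | 35.3% |
| 40% | 83.3% | 76.8% | 68.5% | 58.0% |

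Two leavers cost 11.9, 16.9 and 14.8 points at the three rates.

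**Step 3: leavers carry half the Cycle 1 risk.** Each leaver's event probability is q = 1 − (1−p)^0.5. At p = 0.30, q = 1 − √0.70 = 0.163.

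- One leaver: (1−q) × P(≥3 of 9) + q × P(≥2 of 9) = 0.837 × 0.537 + 0.163 × 0.804 = 0.581.
- Two leavers: (1−q)² × P(≥3 of 8) + 2q(1−q) × P(≥2 of 8) + q² × P(≥1 of 8) = 0.700 × 0.448 + 0.273 × 0.745 + 0.027 × 0.942 = 0.542.

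Two half-risk leavers give 26.6%, 54.2% and 77.3% at true rates of 20%, 30% and 40%: losses of 5.7, 7.5 and 6.0 points. With three quarters of the risk, the figures are 29.5%, 58.2% and 80.6%: losses of about 3 to 4 points.

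**Step 4: does the pause sentence close the gap?** At the planned 1–2 patients per month (Section 11.1), ten patients take 5 to 10 months to enter, so a condition tied to quick accrual may never apply. If it does apply, a patient who leaves without an event has neither completed a cycle nor had an event, and the text gives no outcome for that case. What counts as completing a cycle is also not defined against the omissions in Section 8.3c.

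**The case against.** The strongest reply is that Section 11.5 already shows whom it has in mind: ten patients who each complete Cycle 1 or have an event. Counting leavers as event-free is an inference from Sections 11.2b and 11.4, which do not mention the run-in. A reader might infer that the plan sets no minimum observation at all; the pause sentence does not support that. It remains true that the sentence is conditional and silent on the patient who does neither.

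Next, leaving treatment does not end observation. The study calendar continues toxicity notation off treatment until acute events resolve, and expedited reporting of serious events runs for 30 days after the last dose, which covers a 28-day cycle even after a single Day 1 infusion. This stands in part. The calendar shows no blood counts or chemistry in its off-treatment columns, and its footnote ties them to each infusion. Two of the six listed event categories (persistent Grade 4 cytopenia and Grade 4 liver tests) depend on those samples. Follow-up also cannot supply exposure that never happened.

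A reader might treat leavers as unexposed and take 12–17 points as the expected cost of two exits. The documents do not support this. Everyone in the cohort has been treated, Section 7.1a says infusion reactions are most common at the first administration, and Section 3.1b gives an 18-day half-life. The zero-risk figures are a worst case.

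Early exits may also be few. Hematologic progression needs two consecutive determinations, organ progression alone does not require removal, and listed Grade 4 cardiac events count whatever their cause. Eligibility limits cardiac severity, with "NT-proBNP ≤ 8500 pg/mL within 28 days prior to registration" among the limits. The median survival of 3–6 months in Section 2.1 is historical and concerns advanced cardiac involvement, so it says nothing about exit rates here.

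Finally, one might argue that with four of ten gone and two events among the other six, the rule passes a 33% rate. That turns a count rule into a proportion rule the protocol never states, on six patients and with more exits than there is reason to assume. The trigger also only closes accrual temporarily, and serious events are reviewed separately as they occur.

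**Conclusion.** The gap holds. Section 11.5 bases the continue decision on a count among ten treated patients, has no evaluability or replacement rule for the run-in, and makes its only observation condition depend on fast accrual. Under the plan's general evaluability rule, an early non-toxicity leaver counts as event-free and the trigger becomes less sensitive.

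At an assumed 30% true rate, detection falls from 62% to between 54% (no risk carried) and 58% (half the risk carried) with one leaver, and to between 45% and 54% with two. These ranges rest on assumed exit numbers, toxicity rates and risk shares. Without documented rates, the expected loss cannot be fixed, and it is nil if nobody leaves early. The direction is certain whenever someone leaves with reduced exposure or observation.

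**What to change.** In Section 11.5, base the continue decision on the first ten patients who either had a listed event in Cycle 1 or were observed to the end of Cycle 1 with a minimum exposure. The sponsor should state that minimum and make it consistent with Section 8.3c. Apply this whether or not accrual is fast.

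Replace, in the run-in count only, patients who leave or miss doses for reasons other than toxicity and so do not meet the definition. Do not replace patients who die or who stop for any toxicity, listed or not. They keep their place among the ten and are reviewed individually in the continue decision. Otherwise the repair would remove the very patients the run-in is meant to notice.

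All treated eligible patients stay in the response and toxicity analyses under Sections 11.2b and 11.4. It would also help to print the trigger probabilities for a few true event rates.

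The cost is a few sentences and a later decision. At 1–2 patients per month, a replacement takes about half a month to one month to enter, plus one 28-day cycle: roughly one and a half to two months each, or less if the next patient is already on treatment. Total sample size does not change, because replacements come from the 39 patients already planned.
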